10.1 Appendix 1: Definition of benefit for individual endpoints

Measurement	Endpoint	Direction of benefit*
Spirometry	FVC	Increase
Lung Volumes	TLC	Increase
Diffusion lung capacity	DLCO	Increase
Commercially Confidential Information		
6MWT	6MWD	Increase
	Borg dyspnea score	Decrease
Commercially Confidential Information		

* In the direction of

10.2 Appendix 2: Implementation of the sensitivity analyses

This appendix is adapted from Ratitch, B. and O'Kelly, M. (2011).

SAS PROC MI permits to perform control-based imputation. In this appendix, we will assume that data are stored in a SAS dataset, DIN, with the following variables:

- SUBJID – subject identification number
- SOC_TYPE - stratification factor (with 0 representing no background therapy, 1 nintedanib, 2 pirfenidone)
- SOC_T1 - stratification factor (with 1 representing nintedanib and 0 other cases)
- SOC_T2 - stratification factor (with 1 representing pirfenidone and 0 other cases)
- DRUGNUM - treatment arm (with 0 representing control arm, and 1 representing the Active group)
- BASE, W5, W9-W49, corresponding to the criteria at BASE(baseline), and post-baseline visits W5 (week 5), W9 (week 9) up to W49 (week 49) by 4 weeks
- LASTVIS – last study visit (takes values 0 through 49)

A- General MAR-based multiple imputation

If a dataset has some subjects with non-monotone missingness, the most frequently used imputation method in PROC MI is based on the Markov Chain Monte Carlo methodology and assumes a multivariate normal distribution over all variables included in the imputation model. For datasets with monotone missingness, a number of different methods are available for continuous as well as categorical variables, including some parametric and non-parametric methods. Fortunately, standard software facilitates using the MCMC method to impute data only partially – just enough to obtain a dataset with monotone missingness. Then the remaining missing items can be imputed using other available methods if deemed more suitable. This two-step procedure is the one we use, and is illustrated below using the example dataset described in Section 3 and above in this appendix.

In PROC MI the MCMC method is used to partially impute non-monotone data with the `impute=monotone` option to obtain a dataset with monotone missingness.

```
proc mi data=DIN out=DIN_MONO nimpute=1000 seed=123181;
  var DRUGNUM SOC_T1 SOC_T2 BASE W5 W9-W49;
  mcmc chain=multiple impute=monotone nbiter=200 niter=100;
run;
```

Note that the SOC type factor is dichotomized in 2 continuous variables as in this first call only numeric variable can be used.

Values of the MCMC parameters NBITER (the number of MCMC updates allowed for the sampler to converge to the posterior distribution, and NITER (the number of iterations between each saved draw from the posterior) may need to be increased to allow the MCMC estimates stabilize.

Assumptions underlying this partial imputation step would be of the MAR type, i.e., that subjects with intermediate missing data follow the same model as other subjects in their respective treatment arm that continue the study. This is a reasonable assumption for this partial imputation process because subjects tend to miss intermediate visits due to scheduling conflicts or other reasons generally unrelated to their medical condition under study.

If the proportion of non-monotone missing data is small compared to the number of subjects that discontinue from the study permanently, imputing these few non-monotone values using the partial MCMC method under MAR assumptions would have a small impact on the overall analyses. Note that we will use 1000 imputations. This number is much larger than the default in most software packages. This high number of imputations decrease at the best the uncertainty of the imputation and using as many as 1000 or so imputations does not present any computational difficulties with the current technology.

The output data set DIN_MONO from the above call to PROC MI can now be used as input to a subsequent call of PROC MI to impute the remaining monotone missing values. Since dataset DIN_MONO already contains 1000 copies of the data with partial imputations, the subsequent call to PROC MI will use a BY _Imputation_ statement and request one imputed dataset (n_impute=1 option) within each BY group. This second call will be based on a Not Missing At Random (NMAR) approach as described in B part.

B- NMAR data imputation

Reference-based pattern imputation (unconditional reference)

Assuming that non-monotone missing data have already been imputed using the MCMC method as described above we will then break the imputation process into a sequence of MIs, where each MI is intended to impute missing values at one time-point only, as follows.

- i. In order to impute missing data at time-point 1 (W5) and based on the definition of the link function, first prepare an input dataset, making sure that it will contain only the intended donor pattern (P1: control subjects with non-missing values) and recipient patterns (P2: control arms with missing data and P4 active group with missing data). Separate the input dataset DIN_MONO into two datasets: DIN_MONO_IMP1, containing all control subjects and those subjects from the active group that have values at W4 missing (patterns P1, P2 and P4); and DIN_MONO_REST1, containing the subjects from the active group with non-missing values (pattern P4).

```
data DIN_MONO_IMP1  DIN_MONO_REST1;
  set DIN_MONO;
  *** subjects from the VAY736 non-missing values at W5 ***;
  if DRUGNUM=1 and LASTVIS>=5 then output DIN_MONO_REST1;
  ***All other included VAY736 with missing W5 ***;
  else output DIN_MONO_IMP1;
run;
```

- i. Call PROC MI to impute missing data at time-point 1 using dataset DIN_MONO_IMP1 as input.

```
proc mi data= DIN_MONO_IMP1 out= DIN_REG_IMP1 nimpute=1  
seed=234;  
  by _Imputation_;  
  var SOC_TYPE BASE W5;  
  monotone regression (W5 = SOC_TYPE BASE);  
run;
```

Note that treatment arm is not included as an effect in the model (it is not included in the VAR statement). Since subjects from the active group with non-missing values at time-point t are not included in the input dataset, they will not contribute to the estimation of an imputation model for time-point t. The imputation model will be estimated using control subjects only, while this call to PROC MI will impute missing data at time-point t for all subjects who need imputation at that time-point. This way, subjects from active group will be imputed based on the control subjects' model.

- ii. Assemble a dataset containing all subjects while including the just-imputed visit t data so that they can serve as predictors for the imputation of the next visit.

```
data DIN_IMP1;  
  set DIN_REST1 DIN_REG_IMP1;  
run;
```

- iii. Repeat steps (i)-(iii) for all other time-points sequentially using a reconstructed dataset (e.g., DIN_IMP1) as a starting point in step (i).

C- Modelling on M complete datasets

Once all missing data has been imputed then an ANCOVA of the change from baseline of FVC (CHANGE) at week 49 visit will be applied by _Imputation_ as per model below:

```
proc mixed data=DIN_FULLIMP;  
  by _Imputation_;  
  where VISIT='Week 49'  
  class DRGNUM SOC_TYPE;  
  model CHANGE = DRGNUM SOC_TYPE BASE / s ddfm=kr;  
  
  lsmeans DRGNUM / diff=control('0') cl;  
  ods output Diffs=DIFF_MI LSMeans=LSM_MI;  
quit;
```

D- Pooling analysis

Once the result by Imputation are computed then the parameter estimates will be combined as per Rubin (1976, 1987) method using PROC MIANALYZE.

```
proc mianalyze parms=DIFF_MI;  
  modeleffects DRGNUM;  
  stderr STDERR;  
  ods output parameterestimates=MiDIFF;  
run;
```

Commercially Confidential Information

Commercially Confidential Information

Commercially Confidential Information

Commercially Confidential Information

Signatures

Personal Protected Data

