2.3 Exploratory objective(s)

Commercially Confidential Information

Commercially Confidential Information

3 **Investigational plan**

3.1 **Study design**

This is an exploratory (non-confirmatory) randomized, patient-, investigator-, sponsor- blinded, placebo controlled study of VAY736 in IPF patients. This study will investigate the safety and efficacy of 300 mg VAY736 administered s.c. every 4 weeks for 48 weeks. Approximately 58 subjects will be randomized in a 1:1 ratio on top of local standard of care (SOC), to receive VAY736 or placebo. Randomization will be stratified by SOC treatment (3 levels: nintedanib, pirfenidone, or neither). The randomization scheme will be performed separately within each stratum to ensure balance of the treatment groups with respect to the SOC treatment.

A screening epoch of 6 weeks will be used to assess eligibility. The population will consist of patients with IPF following American Thoracic Society (ATS)/European Respiratory Society (ERS)/Japanese Respiratory Society (JRS)/Latin American Thoracic Association (ALAT) diagnostic guidelines, utilizing High-Resolution Computed Tomography (HRCT) and/or surgical lung biopsy (SLB) as medically indicated. A central reader (imaging expert) will review the screening HRCT to validate an accurate diagnosis of IPF; and a central reader (pathology expert) will review any prior SLB, if an SLB was necessary for the diagnosis of IPF (i.e., SLB was obtained in the normal course of a diagnostic evaluation). Once eligibility has been assessed during the screening epoch, eligible subjects will be randomized to one of the two treatment arms.

Randomized subjects will participate in a 48 week treatment epoch,
Comercially Confidential Information

Please refer to the Assessment Schedule ([Table 8-1](#)) for a list of procedures to be performed at each visit. Efficacy assessments will be performed quarterly (Weeks 1, 13, 25, 37, and 49) during the treatment epoch. Safety assessments will be performed at monthly or quarterly intervals during the treatment epoch. HRCT will be performed at screening and again at the end of the treatment epoch.

Comercially Confidential Information

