6.1.3.2 Sensitivity analysis

Missing not at random (MNAR) analysis

Given the severity of disease and the likelihood of some missing data, the analysis will also include approaches to assess treatment under the assumption of missing not at random (MNAR). Missing data will be imputed using methods specific to non-monotone and monotone missing patterns. In a first step, non-monotone missing data will be imputed 1000 times using MCMC method. Then monotone missing data will be imputed by pattern-mixture model (MNAR) performed on the 1000 samples (O'Kelly & Ratitch 2014). A conservative analysis where missing values in the active group are imputed based on the behavior observed in the placebo group (unconditional reference approach) will be used. The objective is to assess if a potential effect observed in the analysis based on MAR assumption is still present when a more conservative procedure is used. The detail of the sensitivity analyses is described in the appendix 2 (section 10.2).

Analysis of potential Covid-19 impact

As primary analysis may exclude some data due to Covid-19, a sensitivity analysis will also include all PD data regardless of protocol deviations linked to Covid-19.

Covid-19 may interfere with study outcomes due to the following:

- Missing visits with missing FVC assessment and/or missing treatment doses due to restriction in travel or closed site. These missing data are considered as missing completely at random therefore introducing no systematic bias in treatment effect.
- Missing visits due to adverse event linked to Covid-19
- Infection by Covid-19.
- Alteration in recruitment after the start of pandemic as some patients might want to avoid participation in the study due to the Covid-19 risk.

The date of when Covid-19 occurred in different countries is tabulated below. Any patient data collected after that date may be confounded by complications due to the pandemic. For example, if a patient has any on-treatment observation collected after the start date for the specific region, that patient's estimated treatment effect is considered potentially affected by the pandemic.

Table 6-1 COVID-19 date

Region/Country	Start Date	End Date
China	01-Jan-2020	End date has not yet been defined
South Korea	20-Feb-2020	End date has not yet been defined
Japan	21-Feb-2020	End date has not yet been defined
Italy	23-Feb-2020	End date has not yet been defined
Rest of the World	01-Mar-2020	End dates have not yet been defined

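### The placebo-based MNAR analysis of FVC in SAP Appendix 2 is wrong as written: 8 of its 12 visits have no scheduled FVC, and its code sets VAY736 patients aside by last study visit, not by non-missing FVC

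*SAP*

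**What the plan says.** SAP 6.1.3.2 plans a missing-not-at-random (MNAR) analysis in which "missing values in the active group are imputed based on the behavior observed in the placebo group". It then points to the implementation: "The detail of the sensitivity analyses is described in the appendix 2 (section 10.2"). Part C of that appendix applies the result to the change in FVC at Week 49, so the appendix is the specification for the primary endpoint.

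On visits, Appendix 2 works with baseline and "post-baseline visits W5 (week 5), W9 (week 9) up to W49 (week 49) by 4 weeks". All of these enter the first (MCMC) imputation call. Part B then imputes one time-point after another, beginning with this step: "In order to impute missing data at time-point 1 (W5"). On donors it says: "The imputation model will be estimated using control subjects only".

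The protocol's schedule is different. Section 3.1 states: "Efficacy assessments will be performed quarterly (Weeks 1, 13, 25, 37, and 49").

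On the split in part B, the prose and both code comments set aside VAY736 patients whose value at the time-point is present and send those with a missing value to imputation. The executable line is "if DRUGNUM=1 and LASTVIS>=5 then output DIN_MONO_REST1". LASTVIS is defined only as the last study visit, with values 0 to 49.

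**The concern.** There are two separate faults.

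**Visit grid.** Most of the variables to be imputed have no scheduled FVC in either arm. The MCMC step would have to fill columns in which nobody has a planned value, and several of the placebo regressions, including the first, would have no donors. Part A defends the MCMC step with a condition: "If the proportion of non-monotone missing data is small compared to the number of subjects that discontinue from the study permanently", its effect is minor. On this grid the condition cannot be met, because a patient with all four planned FVC values still has eight gaps before Week 49. This fault would show itself when the code is run. The harm is not a biased number; it is that the visit list would have to be redefined outside the SAP.

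**Routing.** Patients attend every 4 weeks but have efficacy assessments quarterly, so attendance and the presence of an FVC are different things. If LASTVIS is derived from attendance, a VAY736 patient who comes to Week 49 without a valid FVC is set aside as if observed, is never imputed, and has no outcome for the ANCOVA. A placebo patient in the same position is imputed. If such patients tend to be the ones declining, an analysis that the SAP calls conservative would favour VAY736, and no program error would be raised.

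This is the only MNAR check on the primary result in the readable text.

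**Working it through.** **1. The plan's own figure, used as input and not in dispute.** Protocol 11.7 gives SD 250 mL, an effect of 160 mL and 58 patients; 11.4.2 gives a one-sided 10% test.
- n per arm = 2 × (1.2816 + 0.8416)² × (250/160)² = 22.01, rounded up to 23, so 46 in total. 46/0.80 = 57.5, rounded up to 58.
- With 29 per arm, SE = 250 × √(2/29) = 65.65 mL and power = Φ(160/65.65 − 1.2816) = 87.6%, which meets the stated minimum of 80%.

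**2. Visit grid.**
- Appendix 2: weeks 5 to 49 in steps of 4, so (49 − 5)/4 + 1 = 12 variables.
- Protocol 3.1: weeks 13, 25, 37 and 49, so 4. The spirometry row of Table 8-1 has shifted columns in the extracted text but also shows four post-baseline marks.
- No scheduled FVC: weeks 5, 9, 17, 21, 29, 33, 41 and 45, so 8 of 12 (67%). With 58 completers that is 58 × 8 = 464 of 58 × 12 = 696 cells.
- SAP 4.3 defines no visit windows, so off-schedule measurements are not mapped to these weeks.

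**3. The split on a constructed data set.** Assumed: 29 per arm; 6 dropouts per arm, last seen at weeks 9, 17, 21, 29, 33 and 45; 2 VAY736 patients attend Week 49 without FVC; LASTVIS means attendance.
- On the 12-visit grid, week 5 has 0 control donors. The code sets aside 29 of 29 VAY736 patients, and none of them has a week 5 FVC.
- On the 4-visit grid, control donors are 28, 26, 24 and 23, so every regression can be fitted. At Week 49 the code still sets aside 23 VAY736 patients, 2 of them without FVC, and imputes 6. A split on missing FVC imputes 8.

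**4. Size of the routing effect, on the corrected grid, if LASTVIS means attendance.** Assumed: changes at weeks 13, 25, 37 and 49 built from independent equal-variance increments; SD 250 mL at Week 49; 200 mL placebo decline; no true effect; 29 per arm; k patients per arm attend Week 49 without FVC. Missing values are drawn from the placebo regression on baseline and earlier changes (20 imputations), analysed by ANCOVA on treatment and baseline and pooled by Rubin's rules. There are 10,000 replicates per case (Monte Carlo SE about 0.7 mL and at most 0.5 percentage points).

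| Who lacks the Week 49 FVC | Bias as coded, k = 1 / 2 / 3 (mL) | One-sided rejection (nominal 10%) |
|---|---|---|
| The k lowest at week 37 (worst case) | +15.5 / +28.0 / +41.1 | 14.9 / 20.2 / 26.5% |
| Random from the lowest third (10 of 29) | +8.3 / +16.6 / +27.4 | 12.3 / 15.4 / 19.5% |
| Random from the lower half (15 of 29) | +4.8 / +12.5 / +19.5 | 11.8 / 13.2 / 15.5% |
| Unrelated to FVC | −0.6 / +0.3 / −0.3 | 9.8 / 10.4 / 10.4% |

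Routed by missing FVC, all 12 cases lie between −1.1 and +1.3 mL, with rejection of 9.0 to 10.5%. Small-sample degrees of freedom lower the rejection rates by 0.1 to 0.5 points.

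*Hand check of the worst case.* The SD at week 37 is 250 × √(3/4) = 216.5 mL. With independent increments a deficit at week 37 carries forward to Week 49. The expected lowest three of 29 standard normal values are −2.03, −1.60 and −1.35. Dropping the lowest k raises the VAY736 mean by 216.5 × (sum of the k deficits)/(29 − k), using unrounded deficits: 216.5 × 2.03/28 = 15.7; 216.5 × 3.63/27 = 29.1; 216.5 × 4.97/26 = 41.4 mL. These are close to the simulated values.

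**5. With a true effect of 160 mL.** Lowest third: 168 / 176 / 188 mL as coded, against 158 / 157 / 158 mL routed by missing FVC. Worst case: 175 / 188 / 201 mL against 158 / 156 / 156 mL.

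**The case against.** The strongest reply concerns the routing. LASTVIS sits in a data set that otherwise holds only identifiers, treatment, background therapy and the criterion values, and it is on the same week scale as those values. The last visit with a value is therefore a natural reading, and under it the split works once the monotone step is done. The surrounding prose states the value-based rule more than once. The appendix also refers to a data set description in Section 3, which is blacked out and could say more. Part C speaks of complete data sets, so a count of patients in the Week 49 ANCOVA would expose anyone left out. The number of patients who attend Week 49 without FVC, and how they are selected, are assumptions; when the gaps are unrelated to FVC there is no bias. Finally, the code is adapted from a published example, the study is exploratory, and the primary MMRM does not depend on it.

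Most of this stands as a limit on weight. It is why the bias is stated only for the attendance reading. It does not remove the conflict: the readable SAP does not tie LASTVIS to a non-missing FVC, and the executable line disagrees with the text it is meant to implement. A prespecified check should not rest on an unwritten derivation. None of it touches the visit grid, which is explicit. Nor does the adapted origin of the code make it optional, since 6.1.3.2 names the appendix as the detail of the analysis.

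**Conclusion.** The concern holds. The grid error is certain: 8 of 12 imputed variables have no scheduled FVC and no scheduled control donor, so the stated procedure cannot be carried out for FVC. Its consequence is an unplanned redefinition of the visits, not bias.

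The routing error is held with medium confidence because it depends on how LASTVIS is derived. If it means attendance, and an assumed 1 to 3 patients per arm attend Week 49 without FVC, the bias towards VAY736 runs from about +5 mL (1 patient from the lower half) to +41 mL (the 3 lowest at week 37). One-sided rejection then runs from about 12% to 27% against a nominal 10%. If the gaps are unrelated to FVC, or LASTVIS means the last visit with an FVC, the bias is about zero. The primary MMRM and the sample size are unaffected. This should be corrected, but it does not undermine the main analysis.

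**What to change.** In Appendix 2:

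- Replace the four-weekly variables by W13, W25, W37 and W49 throughout, including the MCMC call and the part B sequence.
- At each time-point, send VAY736 patients to imputation when FVC is missing at that time-point. Equivalently, define LASTVIS as the last visit with a non-missing FVC after the monotone step.
- Clean up the code: read back DIN_MONO_REST1 instead of DIN_REST1; use one name for treatment (DRUGNUM in parts A and B, DRGNUM in C and D); correct the stray W4 and the double use of pattern P4; add the semicolon after the WHERE line; and declare SOC_TYPE as a class variable in the PROC MI regression.

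The cost is a few lines of SAP text and code before database lock. No new data are needed, and the primary analysis does not change.

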6.1.3 Statistical model, assumptions and hypotheses

The following hypothesis will be tested for VAY736+SoC versus Placebo+SoC:

H0: There is no difference or worsening in change from baseline in FVC (L) from baseline to 48 weeks of treatment between VAY736+SoC and placebo+SoC

H1: There is an improvement in change from baseline in FVC (L) from baseline to 48 weeks of treatment between VAY736+SoC and placebo+SoC

Test will be conducted at a one-sided 10% level and 2-sided 80% CI of the estimates will be displayed. Sense of the one-sided test for each criteria is given in table of appendix 1 (section 10.1).

The primary variable, change from baseline in FVC (L) will be analyzed using a Mixed Effects Model for Repeated Measures (MMRM) in the PD analysis set and considering all assessments collected during the treatment epoch. The model will include treatment and visit as fixed effects, standard of care treatment (Nintedanib, Pirofendone, or no treatment) as factor and baseline value as a covariate, treatment-by-visit and baseline-by-visit as interaction terms. The within subject correlation will be modeled using a repeated statement in SAS Proc Mixed with unstructured covariance matrix. In case of non convergence the model, an alternative AR(1) covariance may be implemented. The posterior will be derived as a t-distribution using a PROC MIXED as detailed in section 3. The main comparison will be a contrast between treatment groups at 48 weeks of treatment. This approach assumes data is Missing At Random (MAR).

Commercially Confidential Information

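### MNAR imputation code in SAP Appendix 2 part B omits CLASS for background therapy, so a numeric SOC_TYPE would enter as a 0-1-2 linear score, contrary to the rest of the SAP

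*SAP*

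**What the plan says.** The variable list in SAP Appendix 2 (section 10.2) defines "SOC_TYPE - stratification factor (with 0 representing no background therapy, 1 nintedanib, 2 pirfenidone". These are three nominal categories. The list does not say whether the variable is numeric or character.

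The same factor is then handled in four places:

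- **Primary MMRM (SAP 6.1.3):** "standard of care treatment (Nintedanib, Pirofendone, or no treatment) as factor".
- **Appendix 2 part A (MCMC step):** two 0/1 indicators, SOC_T1 and SOC_T2, with the explanation "Note that the SOC type factor is dichotomized in 2 continuous variables as in this first call only numeric variable can be used".
- **Appendix 2 part B (reference-based imputation):** SOC_TYPE itself, in "var SOC_TYPE BASE W5" and in "monotone regression (W5 = SOC_TYPE BASE". The call is printed from PROC MI to RUN and contains no CLASS statement. Step iii has it repeated at each later time-point.
- **Appendix 2 part C (ANCOVA on the completed data):** categorical, through "class DRGNUM SOC_TYPE".

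SAP 6.1.3.2 gives this analysis its purpose: to see whether an effect found under MAR persists under a more conservative treatment of the missing data.

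**The concern.** PROC MI treats a numeric variable outside CLASS as continuous. With codes 0, 1 and 2, part B would then fit one slope for background therapy. Pirfenidone versus none would be forced to equal exactly twice nintedanib versus none, an ordering that nothing in the plan supports. Exchanging the labels 1 and 2 would change the imputed values. The imputation model would also be more restrictive than the analysis model applied to its output.

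Part B is the step that creates the MNAR values. At stake is whether the one planned check on the MAR assumption imputes the values that the SAP intends.

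**Working it through.** The plan states no figure on this point, so there is nothing to reproduce. The check compares the code with the rest of the SAP (above) and then sizes the consequence.

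**Inputs from the documents.** 58 patients randomised 1:1, so 29 per arm; SD 250 ml; design effect 160 ml (Protocol 11.7). FVC at weeks 1, 13, 25, 37 and 49 (Protocol 3.1), so the printed W5 call is only a template and any effect acts through the repeated steps at weeks 13 to 49.

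**Inputs assumed.** Mean change and share by stratum are not given. Assume placebo patients on no drug decline g = 50 to 150 ml more than those on either drug, with shares (none/nintedanib/pirfenidone) from 20/40/40 through equal to 40/30/30. Take 20% missing, borrowing the replacement threshold in Protocol 11.7; it is not a dropout forecast.

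**Misfit of the linear score.** Fit the three stratum means m0, m1, m2 on scores 0, 1, 2 by least squares with weights p0, p1, p2. The error (fitted minus true) in each stratum is

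e = k × (1/p0, -2/p1, 1/p2), with k = -(m0 - 2·m1 + m2) / (1/p0 + 4/p1 + 1/p2).

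For means (-g, 0, 0) relative to either drug, the numerator is g.

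| Shares | Denominator | None | Nintedanib | Pirfenidone |
|---|---|---|---|---|
| 20/40/40 | 5 + 10 + 2.5 = 17.5 | +0.286g | -0.286g | +0.143g |
| Equal | 3 + 12 + 3 = 18 | +0.167g | -0.333g | +0.167g |
| 40/30/30 | 2.5 + 13.33 + 3.33 = 19.17 | +0.130g | -0.348g | +0.174g |

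Over g = 50 to 150 ml:

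- None: 0.130 × 50 = +7 to 0.286 × 150 = +43 ml.
- Nintedanib: -0.286 × 50 = -14 to -0.348 × 150 = -52 ml.
- Pirfenidone: 0.143 × 50 = +7 to 0.174 × 150 = +26 ml.

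These apply to patients missing from the first post-baseline visit on; later dropouts are also imputed from their own earlier FVC. If the means are equal or equally spaced, m0 - 2·m1 + m2 = 0 and the misfit is zero.

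**Dependence on labels.** With equal strata and g = 100 ml, the errors for none/nintedanib/pirfenidone are +17/-33/+17 ml. With codes 1 and 2 exchanged they are +17/+17/-33 ml.

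**Effect on the treatment contrast.** Part B imputes missing patients in both arms from the same control-based model. Let a and b be the missing fractions in a stratum on VAY736 and placebo. The shift is then the sum over strata of p × (a - b) × e, taking placebo donors in proportion to the shares.

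- Same dropout in both arms within each stratum: a - b = 0, so the shift is 0.
- Dropout higher in one arm by the same amount in every stratum: the sum of p × e is k × (1 - 2 + 1) = 0, so the shift is 0.
- Extreme case: 40/30/30, g = 150 ml, no placebo dropout, and all missing VAY736 patients (20% of the arm) on nintedanib. That is 0.20/0.30 = 67% of that stratum. Shift = 0.30 × 0.67 × (-52.2) = -10.4 ml; with g = 100 ml it is 0.20 × (-34.8) = -7.0 ml.

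For scale, the standard error of the difference is 250 × √(2/29) = 66 ml.

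**Simulation.** Sequential control-based imputation at weeks 13, 25, 37 and 49 (conditional means, 29 per arm, shares 30/35/35, true effect 160 ml, 4000 trials per scenario) covered four patterns of stratum means. Dropout was 20% throughout, or 45% on nintedanib and 5% elsewhere, the same in both arms. The linear and categorical codings differed on average by at most 0.4 ml in all eight scenarios. Within single trials the difference had an SD of 5 to 9 ml, and 95% of trials changed by less than 11 to 18 ml. The scatter was 5.4 to 6.8 ml even when all stratum means were equal, so much of it is estimation noise and not bias.

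**The case against.** The strongest defence is that the intended model is not in doubt. The factor is nominal everywhere else, no text proposes a score, and the appendix is adapted, illustrative code. It cannot run end to end as printed: it reads DIN_REST1 where DIN_MONO_REST1 was created, mixes DRGNUM with DRUGNUM, and lacks a semicolon after the WHERE clause. It must be rewritten before use. That stands, but repairing those slips would not reveal this one.

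A reader might infer that the call is certain to run without any message. The documents do not support that. Silent running needs numeric storage, which the 0/1/2 coding suggests but the SAP does not state. The part A remark about numeric variables in the first call could mean that SOC_TYPE is a character variable later; PROC MI should then stop.

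A reader might also infer that imputed FVC is wrong in every stratum, or that dropout differing by background drug is enough to bias the treatment comparison. The first depends on stratum means that the documents do not give. The second fails because both arms are imputed from the same model.

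It is also fair that the trial is declared exploratory and that the primary MMRM is untouched.

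**Conclusion.** Wrong as written, minor severity. Part B contradicts parts A and C and the primary model. With a numeric SOC_TYPE the imputation model is mis-specified and depends on labels; with a character one the step should fail. Either way the code needs correcting.

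The reach is limited to the MNAR sensitivity analysis, and the size cannot be known from the documents. The stratum errors of up to about 50 ml rest on the assumed gap and shares and on absence from the first visit on. The average shift in the contrast is about 0 unless dropout differs by both arm and stratum. The 10 ml case needs two thirds of one stratum missing on VAY736 and nobody missing on placebo, and is still small beside a 66 ml standard error.

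**What to change.** Add `class SOC_TYPE;` to every PROC MI call in part B, including the repeats under step iii. Alternatively, replace SOC_TYPE by SOC_T1 and SOC_T2 in the VAR list and the regression, as part A already does. State the storage type of SOC_TYPE in the variable list.

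The cost is one line per call and one extra parameter in each imputation regression. That parameter needs observed placebo patients in all three strata at each visit, which the programmer should confirm with 29 per arm. No data collection or design element changes.
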